7.0 TRIAL PROCEDURES

7.1 Trial Procedures

The Trial Flow Chart - Section 6.0 summarizes the trial procedures to be performed at each visit. Individual trial procedures are described in detail below.

7.1.1 Administrative Procedures

7.1.1.1 Informed Consent

The Investigator must obtain documented consent from each potential participant prior to participating in a clinical trial.

7.1.1.1.1 General Informed Consent

Consent must be documented by the participant's dated signature or by the participant's legally acceptable representative's dated signature on a consent form along with the dated signature of the person conducting the consent discussion.

A copy of the signed and dated consent form should be given to the participant before participation in the trial.

The initial informed consent form, any subsequent revised written informed consent form and any written information provided to the participant must receive the HREC/ERC's approval/favorable opinion in advance of use. The participant or his/her legally acceptable representative should be informed in a timely manner if new information becomes available that may be relevant to the participant's willingness to continue participation in the trial. The communication of this information will be provided and documented via a revised consent form or addendum to the original consent form that captures the participant's dated signature or by the participant's legally acceptable representative's dated signature.

Specifics about a trial and the trial population will be added to the consent form template at the protocol level.

The informed consent will adhere to HREC/ERC requirements, applicable laws and regulations and Sponsor requirements.

7.1.1.2 Inclusion/Exclusion Criteria

All inclusion and exclusion criteria will be reviewed by the investigator or qualified designee to ensure that the participant qualifies for the trial.

7.1.1.3 Medical History

A medical history will be obtained by the investigator or qualified designee. Medical history will include all active conditions, and any condition diagnosed within the prior 10 years that are considered to be clinically significant by the Investigator. Details regarding the bladder

cancer for which the participant has enrolled in this study will be recorded separately and not listed as medical history.

7.1.1.4 Prior and Concomitant Medications Review

7.1.1.4.1 Prior therapy for bladder cancer

The investigator or qualified designee will review and record prior treatment for urothelial cell bladder cancer.

7.1.1.4.2 Concomitant Medications

The investigator or qualified designee will record medication, if any, taken by the participant during the trial. All medications related to reportable SAEs and ECIs should be recorded as defined in Section 7.2.

7.1.1.5 Disease Details and Treatments

7.1.1.5.1 Disease Details

The investigator or qualified designee will obtain prior and current details regarding disease status.

7.1.1.5.2 Prior Treatment Details

The investigator or qualified designee will review all prior cancer treatments including systemic treatments, radiation and surgeries.

7.1.1.5.3 Anti-Cancer Therapy Status

The investigator or qualified designee will review all new anti-neoplastic therapy initiated after the last dose of trial treatment. If a participant initiates a new anti-cancer therapy within 30 days after the last dose of trial treatment, the End of Treatment visit must occur before the first dose of the new therapy. Once new anti-cancer therapy has been initiated the participant will move into follow-up.

7.1.2 Clinical Procedures/Assessments

7.1.2.1 Adverse Event (AE) Monitoring

The investigator or qualified designee will assess each participant to evaluate for potential new or worsening AEs as specified in the Trial Flow Chart and more frequently if clinically indicated. Adverse events will be graded and recorded throughout the study and during the follow-up period according to NCI CTCAE Version 4.03 (see Section 13.2). AEs will be characterized in terms regarding seriousness, causality, toxicity grading, and action taken with regard to trial treatment.

Please refer to section 7.2 for detailed information regarding the assessment and recording of AEs.

7.1.2.2 Full Physical Exam

The investigator or qualified designee will perform a complete physical exam during the screening period. Clinically significant abnormal findings should be recorded as medical history.

7.1.2.3 Directed Physical Exam

For visits that do not require a full physical exam per the Trial Flow Chart (Section 6.0), the investigator or qualified designee will perform a directed physical exam as clinically indicated prior to trial treatment administration.

7.1.2.4 Vital Signs

The investigator or qualified designee will take vital signs at screening, prior to the administration of each dose of trial treatment, at treatment discontinuation and at follow-up as specified in the Trial Flow Chart (Section 6.0). Vital signs should include temperature, pulse, respiratory rate, weight and blood pressure. Height will be measured at screening only.

7.1.2.5 Eastern Cooperative Oncology Group (ECOG) Performance Scale

The investigator or qualified designee will assess ECOG performance status at screening, prior to the administration of each dose of trial treatment and at treatment discontinuation as specified in the Trial Flow Chart (Section 6.0).

7.1.2.6 Tumor Imaging and Assessment of Disease

7.1.2.6.1 Radiological Assessment

Baseline CT Chest/Abdomen/Pelvis will be performed within 42 days of beginning treatment, then at week 19 and 31 prior to the end of treatment visit (+/- 7 days). The scan will be performed with IV contrast unless this is contraindicated due to renal insufficiency.

Imaging before this time point is at the investigators discretion, with the exception of when patients have documented local progression at the time of their first cystoscopy. In this case, patients require a CT scan of chest/abdomen/pelvis within 2 weeks of the cystoscopy.

Patients will have subsequent CT C/A/P restaging at week 19 (+/- 7 days), week 31 (+/- 7 days) and then within 28 days of each scheduled follow up visit.

7.1.2.6.2 Cystoscopic Assessment

Assessment of disease with cystoscopy will take place within 42 days of commencement.

The initial re-evaluation will take place 12 weeks (week 19 of trial) after completing chemoradiotherapy (+/- 7 days) (week 19 of the trial). Evaluation will include urine cytology, rigid cystoscopy, tumour site biopsy if indicated and bimanual examination after TUR.

The second check cystoscopy is mandatory at 24 weeks after completing chemoradiotherapy (+/- 7 days) (week 31 of the trial). Evaluation will include urine cytology, rigid cystoscopy, tumour site biopsy if indicated and bimanual examination after TUR.

In follow up, patients will receive cystoscopic assessment every 3 months for 12 months after week 31, then 6 monthly for 18 months, then 12 monthly until 3 years after the last patient is registered.

Any additional cystoscopic assessment (ie 6 weeks post chemoradiotherapy) is at the clinician discretion.

At the cystoscopic assessments for response (weeks 19 and 31), patients will be determined to have either achieved a Complete Response, Partial Response, Stable Disease or Progressive Disease. The determination will be based upon the results of the urologist assessment of the bladder at cystoscopy, histological parameters and result of most recent systemic imaging, as follows.

Patients will be considered as having a **complete response**, or pT0 response, when: i) the bimanual examination under anesthesia is negative, ii) all the biopsies are negative for any tumor at the site(s) of the pretreatment tumor(s), and iii) there is an absence of metastatic disease on the most recently performed systemic imaging.

Patients will be considered to have a **partial response**, when patients have a lower T stage (depth of invasion of tumour) on tumour biopsy than pretreatment tumour T stage and there is an absence of metastatic disease on the most recently performed systemic imaging.

Patients will be considered to have **stable disease** when patients have the same T stage (depth of invasion of tumour) on tumour biopsy compared to pretreatment tumour T stage and there is an absence of metastatic disease on the most recently performed systemic imaging.

Patients will be considered to have **progressive disease** where there is a higher T stage (depth of invasion of tumour) on tumour biopsy compared to pretreatment tumour T stage or distant metastatic disease, or locoregional nodal involvement on the most recently performed systemic imaging or there is the requirement for intravesical therapy.

Table 8: Determination of response to chemoradiotherapy

	Cystoscopic appearance	Histological Grade	Distant Metastatic Disease on Systemic Imaging*	Nodal Involvement ⁽¹⁾	Initiation of any new anticancer therapies (including Intravesical Therapy)
Complete Response (all conditions satisfied)	Bi-manual examination under anesthesia is negative (required at first and second cystoscopy)	All biopsies negative for active tumour	Absent	Absent	
Partial Response (all conditions satisfied)		Lower T stage	Absent	Absent	
Stable Disease (any condition satisfied)		Same T stage	Absent	Absent	
Progressive Disease (any condition satisfied)		Higher T stage	Present	Present	Administered

⁽¹⁾ Single or multiple regional lymph node metastasis in the true pelvis (hypogastric, obturator, external iliac or presacral lymph node). All other nodes above the aortic bifurcation are considered distant lymph nodes.

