3.2 Secondary Objectives, Hypothesis & Endpoint

Objectives:

- (1) To evaluate the efficacy of the addition of pembrolizumab to concurrent chemoradiation regimen by estimating the complete response rate (see below).
- (2) To characterize:
 - a. overall survival (OS);
 - b. metastatic disease-free survival (MDFS); and
 - c. locoregional progression free survival (LRPFS).

Hypothesis: The addition of pembrolizumab will improve the efficacy of chemoradiation in patients with bladder cancer.

Endpoints:

- (1) Best response, defined as the better of the responses achieved at either the 1st or 2nd cystoscopic examination after completing therapy. (The 1st and 2nd cystoscopic

examinations take place during weeks 19 and 31 respectively of the trial.) See section 7.1.2.6.2 for definitions of the response levels.

(2) Dates of

- i) death,
- ii) detection of metastatic disease,
- iii) detection of locoregional progression,
- iv) any initiation of any new non-protocol anti-cancer therapy

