Cystoscopic assessment will be undertaken 12 weeks and 24 weeks after completion of chemoradiotherapy. This involves examination under anesthesia, cystoscopy and biopsy of all previously positive tumor sites that is utilized to evaluate the tumor status (response) following completion of chemoradiotherapy. In some patients radiographic or cystoscopic evaluation will reveal abnormalities at the bladder tumor-site (such as thickening of the wall, ulcerations, or possible nodularities) which contain no identifiable tumor cells histologically.

Patients will be considered to have had a complete response, or pT0 response, when: i) the bi-manual examination under anesthesia is negative; ii) all the biopsies are negative for any tumor at the site(s) of the pretreatment tumor(s) **and** iii) there is an absence of metastatic disease on the most recently performed systemic imaging.

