These goals can be achieved with a sample size of 30 patients. Consider a Simon's two stage design whereby accrual will be halted if we see greater than 5 UT's amongst the first 10 patients and greater than 11 amongst the first 30 patients. Given these stopping thresholds, if the true underlying UT rate is 0.3 then the cumulative probability of concluding unsafe after stage 2 of accrual will be 17% and if the true underlying rate of UT is 0.5 then the cumulative probability of concluding unsafe after stage 2 of accrual will be 90%. The relationship between the true underlying UT rate and the probability of concluding unsafe is shown in Figure 2.

[figure not shown]

Figure 2: Probability of concluding unsafe as a function of true underlying UT rate

As a secondary objective, we desire to test for an initial signal of efficacy by estimating the proportion of patients achieving a best response of complete response (CR). (See sections 3.2 and 7.1.2.6.2 for the definition of best response.) Similar to the procedure for placing thresholds on the number of UT's we define a threshold for the minimum number of CR's that must be seen in the sample in order to consider the regimen worthy of further investigation on the basis of efficacy. We also define a "maximum uninteresting" true underlying CR rate – the true underlying CR rate at or below which we would not consider the regimen clinically worthy of implementation, and a "minimum interesting" true underlying CR rate – the true underlying CR rate at or above which we would consider the regimen clinically worthy of implementation. We define the maximum uninteresting and the minimum uninteresting rates as being 0.5 and 0.7 respectively. If we place the decision threshold at 18 CR's out of 30, then the probability of judging the regimen worthy of further investigation for efficacy if the true underlying CR rate is 0.5 is 10%, and the probability of judging the regimen worthy of further investigation for efficacy if the true underlying CR rate is 0.7 is 84%. This is illustrated in Figure 3.

[figure not shown]

Figure 3: Probability of further investigation as a function of true underlying CR rate.

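### The CR definition in 8.1 omits new anticancer therapy and regional nodes and limits biopsies to the original tumour site; Table 8 differs on all three, and no precedence is stated

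*Combined protocol and SAP*

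**What the plan says.** Section 8.1 defines CR (pT0) by three conditions: a negative bimanual examination, "all the biopsies are negative for any tumor at the site(s) of the pretreatment tumor(s"), and no metastatic disease on the latest imaging. The prose of 7.1.2.6.2 gives the same three. Neither mentions new anticancer therapy, and neither names regional nodes.

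Table 8, in the same section 7.1.2.6.2, asks for all biopsies to be negative without limiting the site, and for nodal involvement to be absent. One column is headed "Initiation of any new anticancer therapies (including Intravesical Therapy"); in the PD row it reads as administered, and any single condition is enough for PD. The PD prose is narrower on therapy: after T stage, nodes and distant disease it adds only "or there is the requirement for intravesical therapy".

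Section 3.2 defines best response as "the better of the responses achieved at either the 1st or 2nd cystoscopic examination after completing therapy", with the examinations at weeks 19 and 31. Section 8.2 refers to 3.2 and 7.1.2.6.2 for that definition and sets the efficacy rule: "If we place the decision threshold at 18 CR's out of 30".

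**The concern.** Section 7.1.2.6.2 intends each patient to fall into one of four categories at each cystoscopy, but the definitions allow one patient to meet two of them. The difference runs one way: the 8.1 wording accepts patients whom Table 8 rejects. Under 8.1, a pT0 finding after non-protocol therapy, or alongside tumour elsewhere in the bladder, counts as a response to the trial regimen.

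The setting is plausible. Protocol treatment ends at week 19, the second cystoscopy is at week 31, and 5.4.2 prohibits no therapies in post-treatment follow-up. OS, DMFS and LRPFS are only described by Kaplan-Meier curves (8.3), so the formal efficacy judgement rests on the CR count. Left as it is, the analyst must choose between two written definitions when the data are already known.

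**Working it through.** **1. The definitions side by side**

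| Feature | CR in 8.1 and prose of 7.1.2.6.2 | CR row, Table 8 | PD row, Table 8 |
|---|---|---|---|
| Biopsies | negative at pretreatment site(s) | all negative | higher T stage |
| Regional nodes | not named | absent | present |
| Distant disease | absent | absent | present |
| New anticancer therapy | not mentioned | blank in the text available | administered |
| How conditions combine | all | all | any one |

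The blank cell may be a loss in text extraction, so nothing here rests on it. If it held an exclusion, the conflict with 8.1 would be more direct.

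**2. Three patients**

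- *New therapy after week 19; at week 31 the bimanual examination and biopsies are negative and imaging is clear.* CR under 8.1. PD under Table 8.
- *Tumour only at a new bladder site, original site clear, imaging clear.* CR under 8.1. Not CR under Table 8: partial response if the T stage is lower, stable disease if the same. It is PD only if the T stage is higher or therapy is required or given.
- *Bladder clear, pelvic node involved.* PD under Table 8. Under 8.1 the answer depends on whether metastatic disease is read to include regional nodes, which Table 8 puts in a separate column.

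Taking the better of two visits does not settle the first case. Even if week 19 was PD, the week-31 category decides best response, and that category is the disputed one.

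**3. The plan's own figures**

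Inputs from 8.2: n = 30, with rates given as "We define the maximum uninteresting and the minimum uninteresting rates as being 0.5 and 0.7 respectively". The false-go probability is stated as 10% and the power as 84%.

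Formula: P(X ≥ r) = Σ from x = r to 30 of C(30, x) p^x (1 − p)^(30 − x).

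- r = 19: 0.1002 at p = 0.5 and 0.8407 at p = 0.7. This reproduces 10% and 84%.
- r = 18: 0.1808 and 0.9155. This does not.

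Section 8.2 describes the threshold as the "minimum number of CR's that must be seen in the sample", which reads as 18 or more, but its probabilities need 19 or more. That is a separate matter; r = 19 is used below.

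**4. Sensitivity to misclassified patients (assumed numbers)**

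If k non-responders are counted as CR, a go needs only 19 − k true CRs. At p = 0.5:

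- k = 0: 0.1002
- k = 1: 0.1002 + C(30, 18)/2^30 = 0.1002 + 0.0806 = 0.1808
- k = 2: 0.1808 + C(30, 17)/2^30 = 0.1808 + 0.1115 = 0.2923

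If instead a fraction m of non-responders is affected, the counted rate is 0.5 + 0.5m and P(X ≥ 19) is:

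- m = 1% (0.505): 11.0%
- m = 2% (0.51): 12.1%
- m = 10% (0.55): 23.3%

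**The case against.** The strongest reply is that 8.1 is a summary. Section 8.2 sends the reader to 7.1.2.6.2, which presents four alternative categories and makes CR need every condition and PD only one, so PD would naturally override. Other text points the same way. Non-protocol therapy is an event for both DMFS and LRPFS (8.3), and 7.1.6.2 directs effort at disease status until new therapy starts. On this view a clarifying sentence is missing, but the endpoint is not in doubt.

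The likely intent can be granted. The text still does not deliver it: the prose of 7.1.2.6.2 repeats the three-condition CR, no precedence is written, and the only selection rule, in 3.2, favours the better category.

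The biopsy difference is thinner. Section 7.1.2.6.2 calls for tumour-site biopsy if indicated, and 8.1 describes biopsy of previously positive sites, so all biopsies in Table 8 may often mean the same specimens. The background definition of CR in 4.1.2 also uses the pretreatment-site wording. If the 0.5 and 0.7 benchmarks follow that convention, the site limit inflates nothing relative to them; the documents do not say how 0.5 was derived. This weakens the biopsy part and leaves the new-therapy part untouched.

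**Conclusion.** The conflict stands. Applied as written, 8.1 can give a more favourable CR count than Table 8, and the plan does not say which governs. The clear CR-versus-PD case is new therapy between the two cystoscopies. Tumour at a new site is a CR-versus-not-CR difference, and regional nodes are an ambiguity in 8.1.

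A reader might infer two stronger things that the documents do not support:

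- *That both the therapy and the biopsy differences make a patient CR and PD at once.* New-site tumour normally gives partial response or stable disease under Table 8.
- *That the false-go probability is in fact 18.1% or 29.2%.* Those figures assume one or two affected patients in the trial, and the documents give no frequency. At 1% or 2% of non-responders, also assumed, the figure is 11.0% or 12.1%. Only the direction is certain.

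CR is a secondary endpoint in a 30-patient pilot; the toxicity decision and stopping rule are unaffected. The point should be corrected before the CR analysis, but it does not threaten the primary objective.

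**What to change.** Use one CR definition in 8.1, the prose of 7.1.2.6.2 and Table 8: negative bimanual examination, all biopsies negative, no nodal or distant disease, and no non-protocol anticancer therapy (including intravesical) before that cystoscopy. State that PD takes precedence over the other categories, and that a finding after new therapy cannot upgrade best response.

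If the new-therapy cells of Table 8 for CR, partial response and stable disease are filled with *not administered*, the stable-disease row must also change so that all its conditions are required. It now needs only one, so every patient without new therapy would otherwise qualify as stable disease.

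The cost is wording only. New therapies are already documented at the week-31 visit (5.2.5) and their dates are collected (3.2), so no visits, data or patients are added. The CR rate may come out slightly less favourable. The rule would then agree with how DMFS and LRPFS treat new therapy.

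### Table 8 scores stable disease when any one condition holds, which contradicts the section's own prose and leaves the response levels below CR overlapping

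*Combined protocol and SAP*

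**What the plan says.** Section 7.1.2.6.2 defines four response levels twice, in prose and in Table 8.

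- **SD, table:** "Stable Disease (any condition satisfied". The filled cells are same T stage, distant metastasis absent, nodal involvement absent.
- **SD, prose:** "same T stage (depth of invasion of tumour) on tumour biopsy compared to pretreatment tumour T stage and there is an absence of metastatic disease". The conditions are joined by *and*; regional nodes are not mentioned.
- **CR and PR, table:** "Complete Response (all conditions satisfied" and "Partial Response (all conditions satisfied". Both rows carry the same two absence cells as the SD row.
- **PD, table:** "Progressive Disease (any condition satisfied". The filled cells are higher T stage, distant metastasis, nodal involvement, new anticancer therapy given. The new-therapy cell is blank in the other three rows.
- **PD, prose:** after higher T stage it continues "or distant metastatic disease, or locoregional nodal involvement on the most recently performed systemic imaging or there is the requirement for intravesical therapy". Here *or* is intended, and the table agrees.

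Section 3.2 makes this the source of the first secondary endpoint: "Best response, defined as the better of the responses achieved at either the 1st or 2nd cystoscopic examination", with a pointer to 7.1.2.6.2 for the levels. Section 7.1.2.6.2 expects each patient to be placed in one of the four levels at weeks 19 and 31. No text says whether prose or table governs, or which row applies when a patient meets two.

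**The concern.** An any-condition rule suits PD, where each entry is a sign of progression. It does not suit SD, where two of the three entries record only that something bad is absent. Under the printed label, a patient with new distant metastases but no nodal disease is stable because nodes are absent. A patient with a higher T stage and clear imaging is stable because metastases are absent. Both also meet PD.

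At stake is the breakdown of best response below CR. The summary in section 1.0 plans five sites, and the documents describe no central review of response, so one site could follow the table and another the prose. Section 8.4 also relates immune parameters to response without saying which levels it will use. If it goes beyond CR versus not CR, the same ambiguity carries into it.

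**Working it through.** **The plan's own figure.** Table 8 has no figure of its own. The only stated figures that depend on response are in section 8.2: with a threshold of 18 CRs in 30, a 10% chance of a positive decision at a true CR rate of 0.5 and 84% at 0.7. For X binomial with n = 30:

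- P(X ≥ 19) = 0.1002 at 0.5 and 0.8407 at 0.7, which matches.
- P(X ≥ 18) = 0.1808 and 0.9155, which does not.

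The figures therefore correspond to more than 18 CRs. How 8.2 words that threshold is a separate matter. Here it matters only that the rule counts CRs and nothing else.

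**Enumeration of Table 8.** Inputs are the columns of the table: histology (negative, lower, same, higher T stage), distant metastasis (no/yes), nodes (no/yes), new therapy (no/yes). That gives 4 × 2 × 2 × 2 = 32 profiles, with the bimanual examination taken as negative.

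- PD fails only when T stage is not higher and metastasis, nodes and therapy are all absent: 3 profiles. PD is met by 32 − 3 = 29.
- SD as printed fails only when T stage is not the same and metastasis and nodes are both present: 3 × 2 = 6 profiles. SD is met by 32 − 6 = 26.
- The 3 non-PD profiles all meet SD, so PD and SD together are met by 26 − 3 = 23.

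| Version of the table | PD profiles | PD and SD as printed | Share |
|---|---|---|---|
| Full table (32 profiles) | 29 | 23 | 79% |
| Without new therapy (16 profiles) | 13 | 10 | 77% |
| Full table plus bimanual result (64 profiles) | 58 | 46 | 79% |

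**Which profiles overlap.** Ten of the 32 profiles have exactly one sign of progression: higher T stage only (1), metastasis only (3), nodes only (3), new therapy only (3). All ten also meet SD. The 6 PD profiles that escape SD all have both metastasis and nodal disease, with a T stage other than same. The 2 CR and 2 PR profiles also meet SD, 4 of 4.

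**After relabelling the SD row as all conditions.** SD is met by 2 profiles: same T stage, no metastasis, no nodes, with or without new therapy. The one with new therapy is also PD, so the overlap falls from 23 of 29 to 1 of 29, not to zero. CR and PR profiles that also meet SD fall from 4 of 4 to 0 of 4.

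**Under the SD prose.** Taking metastatic disease to mean distant metastasis, SD is met by 4 profiles (same T stage, no metastasis, nodes either way, therapy either way), and 3 of these are PD. If the term is taken to include regional nodes, the overlap is again 1.

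**CR and PR against PD.** Because the therapy cell is blank in the CR and PR rows, 1 CR profile and 1 PR profile, each with new therapy given, also meet PD. The SD label plays no part in this.

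**The case against.** The strongest reply is that this is a labelling slip which the section itself corrects. The prose directly above the table states SD properly, the four levels are plainly meant to be exclusive, and a literal reading that makes every complete responder stable as well could not be applied in practice. Moreover, no planned analysis uses the split between SD and PD: section 8.1 tests the CR rate, the rule in 8.2 counts CRs, and 8.3 names only the unacceptable-toxicity and CR proportions. Most of this stands and limits the consequence. It does not make the printed rule right, and nothing says that the prose prevails.

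Several stronger readings are tempting but are not supported.

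- *The efficacy result is mis-scored.* The CR row already requires all its conditions, and the SD label turns no PD profile into CR.
- *Best response steers such a patient to SD.* Section 3.2 takes the better of two examinations. It compares visits and does not choose between two rows at one visit. The overlap allows SD to be recorded; it does not direct it.
- *Events in the survival endpoints are lost.* Section 8.3 dates distant metastasis-free and locoregional progression-free survival from detection of events and does not cite Table 8. PD in Table 8 cannot be the locoregional event as it stands, since it includes distant metastasis, which 8.3 makes a censoring event. The PD row is also unchanged by the SD label. Exposure arises only if sites turn to Table 8 because 8.3 does not define local or regional progression further.
- *About four in five progressing patients would be called stable.* The 77% to 79% weights profiles equally. The documents give no profile frequencies.

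**Conclusion.** The inconsistency is real. The printed SD rule contradicts the prose and the parallel CR and PR rows, and it leaves the levels below CR of the first secondary endpoint overlapping: 23 of 29 PD profiles in the full table also meet SD. The counts rest on treating negative biopsies as distinct from a lower T stage and on the table's own therapy condition. The practical effect is confined to how non-CR patients are described, and to any exploratory analysis that uses those levels. The CR rate and its decision rule are not affected by this label. It is worth correcting because the correction is cheap and should precede the scoring of responses, but it is not a threat to the trial's main conclusions.

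**What to change.** Make three edits in section 7.1.2.6.2.

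1. Relabel the SD row of Table 8 with the all-conditions wording already used for CR and PR.
2. Add absence of nodal involvement to the SD prose so that it matches the table.
3. State that a patient who meets both SD and PD at a visit is scored PD at that visit. This settles the one remaining overlap: same T stage, no metastasis, no nodes, new therapy given.

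The cost is one word and two short additions. Sample size and CR count do not change.

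Do not widen the third edit into a general rule that PD overrides every other level. A patient given new anticancer therapy after week 19 who is pT0 at week 31 meets both CR and PD as the table stands. If that patient was not CR at week 19, settling the overlap either way decides whether one more CR is counted. That must be reconciled openly and separately. The CR and PR prose is silent on nodes in the same way as the SD prose, and that belongs in the same reconciliation.

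One side effect needs a line. With the all-conditions label, negative biopsies with a positive bimanual examination and no metastasis, nodes or new therapy fall in no row, unless negative biopsies count as a lower T stage. Such a patient is not CR in any case, but the sponsor should say which level applies.
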